3. STUDY PLAN AND PROCEDURES

This CSP has been subject to a peer review according to AstraZeneca standard procedures.

3.1 Overall study design and flow chart

This is an open-label, randomized, 3-treatment, 4-period, 6-sequence crossover study conducted at a single study center to compare the PK of AZD6244 after oral administration of single doses of white (current Phase II) and blue (planned Phase III) capsule formulations. Volunteers will receive 1 single oral dose of AZD6244 each of Treatment A and Treatment C and 2 doses of Treatment B each separated by washout periods of a minimum of 7 days between doses. Treatment A will consist of three 25-mg AZD6244 white (current Phase II) capsules. Treatment B will consist of three 25-mg AZD6244 blue (planned Phase III) capsules. Treatment C will consist of 35 mg AZD6244 solution.

For Dosing Period 1, 2 volunteers will receive AZD6244 doses at least 2 days before the remainder of the volunteers.

Serial blood samples for the determination of AZD6244 PK will be collected up to 36 hours following the AZD6244 dose. Volunteers will be admitted to the study center on Day -1 and will remain resident until completion of Day 2 procedures for each treatment period. A follow-up visit will be conducted at least 7 days following study center discharge of the volunteer's final treatment.

Safety assessments will include AEs, clinical laboratory assessments (clinical chemistry, hematology, and urinalysis), vital signs (blood pressure and pulse rate), physical examinations, telemetry, pECGs, dECGs, LVEF, and ophthalmology assessments.

Genetic analysis of the genes related to AZD6244 disposition and safety may be performed. Participation in the exploratory genetic sampling is optional for the volunteer.

The study flow chart is presented in [Figure 1](#) and the study plan is presented in [Table 2](#). Specific timing for PK, dECG, blood pressure, and laboratory assessments are in [Table 3](#) and a detailed time schedule for dECG assessments during the residential period is presented in [Table 4](#).

Figure 1 Study flow chart

[figure not shown]

Table 2 Study plan

Assessment	Screening	Dosing Periods 1, 2, 3, and 4^a			Follow-up
Visit	1	2, 3, 4, and 5			6
Days	Day -28 to -2	-1	1	2	At least 7 days after the last dose
Assessment					
Informed consent ^b	X				
Optional pharmacogenetic informed consent ^c	X				
Inclusion/exclusion criteria	X	X			
Demography	X				
Height and calculation of BMI	X				
Weight	X				X
Medical/surgical/smoking history	X				
Hepatitis B, C, and HIV screen	X				
Admission to the study center		X			
Prior/concomitant medications	X	X	X	X	X
Physical examination ^d	X	X		X	X
Eye examination ^e	X				
Laboratory assessments (clinical chemistry, hematology, and urinalysis ^f)	X ^g	X			X
Cardiac biomarkers ^{h,n}	X	X	X		X
Drug screening	X	X			

Table 2 Study plan

Assessment	Screening	Dosing Periods 1, 2, 3, and 4 ^a			Follow-up
Visit	1		2, 3, 4, and 5		6
Days Assessment	Day -28 to -2	-1	1	2	At least 7 days after the last dose
Vital signs (including blood pressure and pulse rate) ^k	X	X	X ^j	X	X
12-lead dECG ^k			X ^l	X	
12-lead pECG	X	X	X ^l	X	X
Telemetry ^m		X ^r	X		
Echocardiogram ⁿ	X	X			X
Randomization			X ^o		
Dose administration			X ^p		
PK blood sampling ^q			X	X	
Optional pharmacogenetic sampling			X ^r		
SAE recording	X	X	X	X	X
AE recording		X	X	X	X
Discharge				X	

^a At least 7-day washout period will occur between each AZD6244 administration.

^b Informed consent will be collected prior to any study-specific procedures being performed.

^c Pharmacogenetic informed consent is required if the subject volunteers for the pharmacogenetic blood sampling. Period 1, Day 1 only.

^d Complete physical examinations will be performed at screening and at follow-up. A brief physical examination will occur on Day -1 and discharge of each treatment.

^e Ophthalmological examination will be performed any time prior to the first dose of IP and on any occurrence of a visual AE.

^f Microscopy will be performed if abnormal urinalysis results.

^g Subjects will fast for 4 hours prior to clinical laboratory evaluations at screening. Creatinine clearance will be estimated using Cockcroft-Gault formula at screening.

- h Includes laboratory assessments for troponin, BNP, CPK, and CK-MB which are to be collected on the same day as the echocardiogram. On Day -1 and at follow-up troponin, BNP, CPK, and CK-MB may be determined as part of the clinical chemistry panel. On Day 1, only troponin, BNP, CPK, and CK-MB will be collected at the sampling times specified in [Table 3](#).
- i Supine blood pressure and pulse rate will be evaluated after the subject has rested in the supine position for at least 10 minutes prior to the evaluation. If possible, the same arm and equipment should be used for each evaluation.
- j Vital signs will be recorded at predose and 1.5, 6, and 24 hours postdose.
- k A 12-lead dECG and vital signs will be performed after the subject has rested in a supine position for at least 10 minutes prior to the evaluation.
- l Digital and paper ECGs will be performed predose and at 1.5, 6, and 24 hours postdose.
- m Telemetry to be performed for 4 hours on Day -1 during Period 1 only. For each period, telemetry will occur approximately 30 minutes predose until 24 hours postdose.
- n Additional cardiac blood biomarkers may be collected along with an ad hoc echocardiogram on occurrence of cardiac AE.
- o Randomization will occur in Dosing Period 1 on Day 1, predose only.
- p Subjects will receive a single dose on Day 1 of Dosing Periods 1, 2, 3, and 4 according to their randomized treatment sequence.
- q Plasma samples will be collected predose and 0.5, 1, 1.5, 2, 4, 6, 8, 12, 24, and 36 hours postdose on Dosing Periods 1, 2, 3, and 4.
- r Period 1 only.

BMI body mass index; HIV human immunodeficiency virus; SAE serious AE.

Table 3 Detailed study plan for Day 1 of Dosing Periods 1, 2, 3, and 4

t (hours)	PK blood collection	dECG	Supine blood pressure	Troponin, BNP, CPK, and CK-MB
0	X	X	X	X
0.5	X			
1	X			
1.5	X	X	X	
2	X			
4	X			
6	X	X	X	X
8	X			
12	X			
24	X	X	X	
36	X			

Table 4 Time schedule for digital ECG (dECG) assessments during residential period

Study Days	ECG Number	Time: Start hour: minute ^a	Dose	Time: Stop hour: minute	dECG continuous ^{bcd}	Other
1		-01:30		-01:00		Apply the electrodes ^c
1		-00:40		-00:30		Rest in bed
1	1	-00:30	Predose	-00:20	10 minutes	
1		-00:20		-00:05		Toilet use recommended
1		00:00	Admin of AZD6244/ placebo			
1	2	01:25		01:30	5 minutes ^d	
1	3	05:55		06:00	5 minutes ^d	
2	4	23:55		24:00	5 minutes ^d	

^a Time points for dECG may be adjusted according to emerging PK data.

^b The subject must be in the same supine body position (maximum 30 degrees flexion in the hip) at each time point and at all visits. Subject's feet should not contact the footboard of the bed.

^c Skin must be cleaned, and electrode positions marked with an indelible pen. Electrodes should be applied at least 30 minutes before first recording.

^d Subject must rest in bed for at least 10 minutes prior to each ECG time point.

Admin administration; dECG digital electrocardiogram; ECG electrocardiogram; PK pharmacokinetic.

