2.2 Secondary objectives

The secondary objectives of this study are to:

- Investigate the safety and tolerability of single doses of AZD6244 in healthy male volunteers
- Estimate within-volunteer variability in the PK of AZD6244
- Establish the relative bioavailability of AZD6244 after oral administration of single doses of blue capsules (planned Phase III) with respect to an oral solution formulation
- Characterize the PK of *N*-desmethyl AZD6244 after oral administration of single doses of AZD6244 white (current Phase II) and blue (planned Phase III) capsules

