The oral solution proposed for use in this study has not previously been administered to humans in a clinical study. The dose for use in study D1532C00066 was selected based upon preclinical experience of the solution performance in both dog and monkey and the bioavailability observed. The relative bioavailability of the capsule formulation compared to the Phase I AZD6244 free base in Captisol[®] suspension (“mix and drink”) was comparable in preclinical studies in dog and in a clinical study in patients (D1532C00005). Therefore the relative bioavailability of the oral solution to the capsule in dog was considered to be predictive of the expected performance in human and this was used to derive a suitable dose. This preclinical relative bioavailability predicted a potential for up to a 2-fold difference in exposure (both C_{max} and AUC), and this also took into account that the oral solution is not dissolution rate limited and a more rapid and complete absorption is possible, resulting in a higher C_{max} . Therefore, in order to minimize the risk of exceeding the mean AUC and C_{max} observed with a 75-mg dose of the AZD6244 capsule formulation, a solution dose of 35 mg (approximately half that of the capsule) was recommended.

For Dosing Period 1, 2 volunteers will receive AZD6244 doses at least 2 days before the remainder of the volunteers.

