11.2 Calculation or derivation of pharmacokinetic variables

The PK analyses of the plasma concentration of AZD6244 amide will be performed. Pharmacokinetic analyses will be conducted according to the following procedures (SOPs) for PK analyses if not otherwise specified.

Pharmacokinetic parameters in plasma will be derived using noncompartmental methods with

Actual elapsed time from dosing will be used for final plasma PK parameter calculations. Pharmacokinetic parameter units will be consistent with the plasma concentration units specified in the bioanalytical data. No conversion of units will be made.

If data permits and unless otherwise stated, the following PK parameters will be determined for AZD6244, *N*-desmethyl AZD6244, and AZD6244 amide, following single-dose administration:

AUC	Area under the plasma concentration-time curve from zero to infinity (AUC, ng*h/mL), calculated by linear up/log down trapezoidal summation
-----	---------------------------------------------------------------------------------------------------------------------------------------------

$AUC_{(0-t)}$	Area under the plasma concentration-time curve from zero to the time of the last quantifiable concentration [$AUC_{(0-t)}$, ng*h/mL], calculated by linear up/log down trapezoidal summation
$AUC_{(0-12)}$	Area under the plasma concentration-time curve from zero to the time of 12 hours [$AUC_{(0-12)}$, ng*h/mL], calculated by linear up/log down trapezoidal summation
C_{max}	Maximum plasma concentration (C_{max} , ng/mL), obtained directly from the observed concentration versus time data
t_{max}	Time to C_{max} (t_{max} , h)
CL/F	Apparent oral plasma clearance (CL/F, L/h, AZD6244 only)
V_{ss}/F	Apparent volume at distribution equilibrium, $MRT*CL/F$ (V_{ss}/F , L, AZD6244 only)
V_z/F	Apparent volume of distribution (V_z/F , L, AZD6244 only)
$t_{1/2}$	Terminal half-life ($t_{1/2}$, h)
λ_z	Terminal rate constant (λ_z , 1/h).

Metabolite to parent drug ratios will be calculated for the primary PK parameters AUC and C_{max} .

The following PK parameters will be calculated for diagnostic purposes and listed, but will not be summarized:

- The time interval (h) of the log-linear regression to determine $t_{1/2}$ ($t_{1/2}$, interval)
- Number of data points ($t_{1/2}$, N) included in the log-linear regression analysis used to determine λ_z . A minimum of 3 data points will be used for λ_z determination

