Primary PK parameters are AUC and C_{\max} of AZD6244. If AUC is not reportable in more than 60% of the 30 enrolled volunteers (ie, 18 reportable AUCs) then $AUC_{(0-t)}$ will be used in the inferential analysis.

Utilizing data from the first three treatment periods only, the relative bioavailability between treatments will be assessed between test (Treatment B) and reference (Treatments A) treatments. Analyses will be performed using a linear mixed-effect analysis of variance model using the logarithm of AUC and C_{\max} as the response variables, sequence, period, and treatment as fixed effects, and volunteer nested within sequence as a random effect. Transformed back from the logarithmic scale, geometric least-squares means together with confidence intervals (CIs) (2-sided 95%) for AUC and C_{\max} will be estimated and presented.

Also, ratios of geometric least squares means together with CI (2-sided 90%) will be estimated and presented.

Using a similar model as above, comparisons will be made for dose-normalized AUC and C_{\max} between test (Treatment B) and reference (Treatments C) treatment. AUC and C_{\max} will be dose-normalized prior to the ln-transformation.

Comparisons include:

- Treatment B versus A
- Treatment B versus C

Using treatment B data only, estimates of between and within-volunteer variability's will be obtained by employing a linear mixed-effect analysis of variance model using the logarithm of AUC and C_{\max} as the response variables and treatment as fixed effect. Volunteer nested within sequence will be a random effect. Treatment will be re-coded as B1 and B2, where B1 will correspond to Treatment B given in the first 3 periods and B2 will correspond to Treatment B given in Period 4. Estimates for the between and within-volunteer variability's will be present together with the associated 90% CIs.

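### The oral solution is sampled on the capsule grid with no draw before 0.5 h, so its Cmax may be under-read and the B/C Cmax ratio inflated

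*Protocol*

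**What the plan says.** Table 2 footnote q and Table 3 (Section 3.1) set one schedule for every dosing period: "Plasma samples will be collected predose and 0.5, 1, 1.5, 2, 4, 6, 8, 12, 24, and 36 hours postdose". Treatments A and B (capsules) and C (solution) therefore share a first postdose draw at 0.5 h.

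On the solution, Section 3.3 states "The oral solution proposed for use in this study has not previously been administered to humans in a clinical study" and that "the oral solution is not dissolution rate limited and a more rapid and complete absorption is possible", with a higher Cmax as the result. It gives no tmax or absorption rate for any formulation.

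Section 11.2 defines Cmax as "obtained directly from the observed concentration versus time data". Section 2.2 lists as a secondary objective: "Establish the relative bioavailability of AZD6244 after oral administration of single doses of blue capsules (planned Phase III) with respect to an oral solution formulation". To serve it, Section 12.2.2 plans that "comparisons will be made for dose-normalized AUC and C_{\max} between test (Treatment B) and reference (Treatments C) treatment".

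**The concern.** The protocol uses the possibility of faster absorption when it chooses the solution dose, but does not carry it into the sampling times. An observed maximum cannot exceed the true peak. If the solution peaks before 0.5 h, the first sample falls on the declining limb and C is read too low. C is the denominator of B/C, so the ratio rises unless B loses as large a share of its own peak. The confidence interval would not reflect such a shift.

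Cmax is where a difference in absorption rate shows most directly, and Section 1.2 says the solution is included to examine formulation effects. Section 3.3 also chose the solution dose to limit the risk of exceeding mean capsule AUC and Cmax. An under-read peak would weaken the study's own check of the Cmax part of that reasoning.

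The loss could not be repaired during the study. Table 5 places C only in Periods 1 to 3, and the interim pharmacokinetic analysis (Section 12.1.3.1) follows Period 3. Two volunteers are dosed at least 2 days ahead in Period 1, but no pharmacokinetic review of them is described. Permission to move time points for emerging data (Table 4, footnote a) concerns digital ECGs. Section 7.1 lets sample numbers change, but explains this by repeat safety samples.

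**Working it through.** **Stated figures first.** Section 12.3 gives a within-volunteer value of 0.13 for Cmax, n = 24, and an upper 80% limit of 1.43 for an observed ratio of 1.25. Reading 0.13 as a log-scale variance, SE = √(2 × 0.13/24) = 0.104. With 44 degrees of freedom, exp(ln 1.25 + 1.301 × 0.104) = 1.431, which reproduces. The 95% power for AUC (variance 0.04, n = 24) comes out at 0.969 for a true ratio of 1.00 and 0.947 for 1.03, so it reproduces within 2 points. Neither figure depends on the sampling times.

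**Yardstick.** With the same SE, the 90% confidence interval of a Cmax ratio is the estimate times or divided by exp(1.680 × 0.104) = 1.19. Applying 0.13 to B versus C is an assumption.

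**Model (all kinetic inputs assumed).** With x = time since dose minus lag, concentration is proportional to w·g(α) + (1 − w)·g(β), where g(k) = ka/(ka − k) × (e^(−k·x) − e^(−ka·x)). Here β = 0.1/h. The capsule has ka 1.5/h and lag 0.3 h; the solution has lag 0.05 h and ka 2 to 15/h. Log-scale SDs are 0.5 for ka and lag and 0.2 for α and β, with 800 profiles per scenario. Captured share = geometric mean of (highest value on the grid ÷ true peak). Bias factor on B/C = share for B ÷ share for C.

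**One profile by hand** (solution, w = 0.85, α = 1.2/h, ka = 15/h):
- At 0.5 h, x = 0.45: g(1.2) = 1.087 × (0.583 − 0.001) = 0.632 and g(0.1) = 1.007 × (0.956 − 0.001) = 0.961. The total is 0.85 × 0.632 + 0.15 × 0.961 = 0.681.
- The true peak, at about 0.24 h, is 0.822. The protocol grid captures 0.681/0.822 = 83%.
- At 0.25 h the value is 0.821, practically the whole peak.

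**Simulation** (factors from unrounded shares):

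| w, α (/h) | Solution ka (/h) | Median solution tmax (h) | C captured | B captured | Factor, protocol grid | Factor, plus 0.25 h | Factor, plus 0.25 and 0.75 h |
|---|---|---|---|---|---|---|---|
| one-phase | 15 | 0.39 | 0.990 | 0.987 | 0.997 | 0.992 | 0.991 |
| 0.7, 0.5 | 4 | 0.71 | 0.986 | 0.991 | 1.004 | 1.004 | 0.996 |
| 0.7, 0.5 | 8 | 0.46 | 0.979 | 0.991 | 1.012 | 1.003 | 1.000 |
| 0.7, 0.5 | 15 | 0.31 | 0.952 | 0.990 | 1.040 | 1.001 | 1.001 |
| 0.8, 0.8 | 8 | 0.40 | 0.957 | 0.989 | 1.033 | 1.006 | 1.005 |
| 0.8, 0.8 | 15 | 0.28 | 0.904 | 0.989 | 1.095 | 1.006 | 1.007 |
| 0.85, 1.2 | 4 | 0.52 | 0.974 | 0.984 | 1.010 | 1.003 | 1.000 |
| 0.85, 1.2 | 8 | 0.34 | 0.916 | 0.984 | 1.074 | 1.005 | 1.010 |
| 0.85, 1.2 | 15 | 0.25 | 0.834 | 0.984 | 1.180 | 1.010 | 1.015 |

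Wherever median solution tmax is 0.5 h or later, the factor is 0.99 to 1.01 in these runs, and 0.99 to 1.02 over a wider set of assumptions. Steeper assumptions than the last row take it to about 1.3. The 0.25 h sample does nearly all the corrective work; adding 0.75 h changes the factor by about 1% or less. Any effect on AUC was not computed.

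**The case against.** The strongest reply is that an early solution peak is not established. Section 3.3 calls faster absorption possible, within a cautious argument about dose, and gives no kinetics. Section 1.2 puts the compound in BCS Class IV at 75 mg, a class marked by low permeability as well as low solubility. A solution removes the dissolution step but not a permeability limit, so the fastest scenarios are the least supported. The capsule also loses 1 to 2% of its peak on this grid. With one-phase decline the factor is 0.997 even at a median tmax of 0.39 h, so the net bias can be nil or slightly downward. B versus C is secondary and has no acceptance limit, and most scenarios lie well inside the 1.19 margin of its interval. The sponsor held dog and monkey data on the solution that are not shown here.

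All of this stands, and it limits the claim to a conditional one. Two further readings are tempting. One is that the protocol expects a faster solution and the ratio is therefore biased upward; the text supports only that it may be. The other is that a missed peak would go unnoticed. Since tmax is derived and summarized, clustering at 0.5 h would be visible. That would signal the problem but would not recover the missing peak values.

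What the reply does not supply is a reason, in the protocol, for a 0.5 h first sample of a solution new to humans that the protocol itself says may absorb faster.

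**Conclusion.** The point holds as a conditional weakness of the design. If the solution peaks before 0.5 h, Treatment C Cmax will be under-read and the dose-normalized B/C Cmax ratio may be inflated. The effect is about nil (factor 0.99 to 1.02) when median solution tmax is about 0.5 h or later. When tmax is clearly earlier and the early decline is fast, it runs from a few percent to about 20 to 30% in the extreme case. At that end the bias is as large as the random error of the comparison (times or divided by 1.19) or larger. The top of the range is set by assumed kinetics and is not a bound derived from the protocol.

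A reader might infer that the formulation comparison as a whole is compromised. The documents do not support that: the primary B versus A comparison involves capsules only, and the stated power is for AUC and does not depend on the early sampling times.

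**What to change.** Add one pharmacokinetic sample at 0.25 h in all four periods, in Table 2 footnote q and Table 3. Applying it to every period keeps the grid identical across treatments; adding it only for C would give C one more chance at a high observed value than B.

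Update Table 7:
- Pharmacokinetic samples go from 44 to 48 (88 to 96 mL).
- Discard volume goes from 44 to 48 mL.
- Added blood is 4 × (2 + 1) = 12 mL, so the total is 326.5 + 12 = 338.5 mL, under the 450 mL limit in Section 7.1.

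The cost is four more small draws and four more samples to assay per volunteer. Volunteers are already resident, no visit is added, and Table 3 schedules nothing else at 0.25 h. A 0.75 h sample is optional and adds little; with both, the total would be 326.5 + 24 = 350.5 mL. If the sponsor prefers to keep 0.5 h, Section 3.3 should give the solution data that justify it.

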3.2 Individual stopping criteria

The individual stopping criteria are:

- Any volunteer who experiences a 10% drop in LVEF from baseline taking the value to below 55% must be withdrawn from the study and referred to a cardiologist for management and monitoring.
- Any volunteer with an AE of dyspnea will be withdrawn from this study. The event must be fully investigated according to the AZD6244 dyspnea algorithm.
- Any volunteer experiencing a visual AE should have a full ophthalmological examination. If a retinal abnormality is identified, volunteers should be withdrawn and an OCT scan performed. All abnormalities should be followed up to resolution. The assessments will be repeated 28 days later to document resolution.
- In the event of a cardiac AE or a clinically significant increase in troponin and CK-MB at the 6 hour postdose time point, the volunteer should have an echocardiogram performed, a follow-up blood sample for troponin, BNP, CPK, and CK-MB taken.

The volunteer must be withdrawn from the study and referred to a cardiologist for management and monitoring.

3.3 Rationale for study design, doses, and control groups

This study will be conducted in healthy, male volunteers to avoid interference from disease processes or other drugs. The selection criteria are defined such that volunteers selected for participation in this study are known to be free from any significant illness.

The study will investigate the differences of 25-mg white capsule formulation in relation to the 25-mg blue capsule formulation of AZD6244. The oral dose of 75-mg AZD6244 (administered as 3 capsules) was selected because 75 mg is the dose level used in the Phase II and the dose identified for the Phase III study. The predicted mean exposure from a single 75-mg (three 25-mg capsules) dose of AZD6244 has been calculated from data from the approximately 1250 patients so far exposed to AZD6244 in clinical studies. Review of the safety and tolerability profile from these advanced cancer patients have indicated that the healthy volunteers are considered unlikely to experience acute significant AEs. [Table 1](#) indicates that acute AEs within the first 24 hours tend to be either low grade and manageable (such as headache) or related to the underlying disease (and hence will not be expected in healthy volunteers). The intensive safety monitoring included in this study will aim to identify any potential AEs early and include specific management algorithms for specific events that have been associated with significant toxicity in cancer patients receiving long-term AZD6244.

The oral solution proposed for use in this study has not previously been administered to humans in a clinical study. The dose for use in study D1532C00066 was selected based upon preclinical experience of the solution performance in both dog and monkey and the bioavailability observed. The relative bioavailability of the capsule formulation compared to the Phase I AZD6244 free base in Captisol[®] suspension (“mix and drink”) was comparable in preclinical studies in dog and in a clinical study in patients (D1532C00005). Therefore the relative bioavailability of the oral solution to the capsule in dog was considered to be predictive of the expected performance in human and this was used to derive a suitable dose. This preclinical relative bioavailability predicted a potential for up to a 2-fold difference in exposure (both C_{max} and AUC), and this also took into account that the oral solution is not dissolution rate limited and a more rapid and complete absorption is possible, resulting in a higher C_{max} . Therefore, in order to minimize the risk of exceeding the mean AUC and C_{max} observed with a 75-mg dose of the AZD6244 capsule formulation, a solution dose of 35 mg (approximately half that of the capsule) was recommended.

For Dosing Period 1, 2 volunteers will receive AZD6244 doses at least 2 days before the remainder of the volunteers.

